6.9.2 Exposure

For Part 1 and Part 2, the number of doses of study treatment administered (total number of occasions that a time of study drug was recorded) and the number of days of exposure to the study treatment ([last date of dosing - first day of dosing] + 1) will be summarised. These data will be obtained from the comfort diary card data.

All study drug dispensing and return data will be listed. The number of vials expected to have been used for each period will be presented. This will be calculated as 2 x (number of days that a subject administered eye drops dependent on date of first and last dose within each period)

where *number* of days that a subject administered eye drops dependent on date of first and last dose within each period is derived from the Study Drug Dispensing and Return CRF page data as "date of last study drug return for the period – date of first study drug dispensing for the period".

6.10 Efficacy Evaluation

6.10.1 Primary Endpoint

The primary endpoint is a safety outcome and is described under section 6.14.1.1.

6.10.2 Secondary Endpoints

6.10.2.1 Post-instillation comfort

Post-instillation comfort scores will only be available for the least comfortable eye. The eye that the scoring was recorded on will not be captured on the eCRF.

A score of 0 to 4 will be recorded at 0.5 min, 1 min, 2 min, 3 min and 5 min each morning and evening on diary card.

The total score over two-week periods for days 1 to 14, 15 to 28, 29 to 42 and 43 to 56 will be calculated for each patient by summing the scores from the five timepoints taken each morning and evening over the 14 days, therefore the total score will have a possible range of 0 to 560. If there are 20 or more missing data points during the period, then the total score will not be calculated and set to missing.

For derived non-missing scores, an average score for the period will also be calculated as follows:

$$Average \ score = \frac{Total \ score}{Number \ of \ non - missing \ days}$$

The average score at each two week-period will be classified as follows: an average total comfort score of < 10 will be deemed to be comfortable/acceptable, 10 - 19 will be moderately uncomfortable, 20 - 29 will be very uncomfortable and ≥ 30 will be severely/unacceptably uncomfortable.

The number and percentage of missing data over the two-week period will be calculated, where 140 data points would expected to be recorded over 14 day period.

Should the five scores not be available at any morning or evening timepoint there will be no imputation, and the total score and classification will be derived for the two-week period for that patient regardless of missing data.

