6.9 Safety and Efficacy Assessments

Safety will be assessed by the Investigator from history and clinical examination. Adverse events (AE) will be recorded in the CRFs and in part 2 of the study, a comparison will be made between the number, type and severity of AEs between the treatment groups.

Comfort will be assessed on the basis of the patient diary cards. A comparison of the total comfort scores between the randomised treatment groups in part 2 of the study, will be made at the conclusion of the trial. For each treatment group a total comfort score of < 10 will be deemed to be comfortable/acceptable, 10 - 19 will be moderately uncomfortable, 20 - 29 will be very uncomfortable and > 30 will be severely/unacceptably uncomfortable.

Composite eye sign and symptom scoring will be carried out by the investigator/blind assessor (depending on the part of the study) at each scheduled clinic visit. Symptoms will be scored by the patient in response to specific questioning by the investigator/blind assessor. Signs will be scored by the investigator/blind assessor as a result of the clinical examination. At each visit the patient will be asked which eye feels to be the worst affected at the time of the visit and that eye will be used for the examination. If both eyes seem to the patient to be equally affected the right eye will always be used. The worst affected eye may change from visit to visit.

For each sign/symptom a numerical score 0 - 3 will be awarded (see table in Section 17.1 (AKC and VKC) and 17.2 (severe allergic conjunctivitis - SAC or PAC). These scores will be summed at the conclusion of the examination and this will be known as the composite score. The minimum possible composite score is 0, the maximum 33 (AKC and VKC) or 27 (severe allergic conjunctivitis (SAC or PAC)). All statistical comparisons, in part 2 of the study, will be done on the basis of the composite score for each patient/visit.

MMP-9 detection using the *Inflammadry*[®] device. This device will give a binary (positive/negative) result which will be recorded in the CRFs at each time point and a comparison of the numbers of positives in each randomised treatment group will be made.

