6 ANALYSIS PLAN

6.1 General

Summary statistics for continuous variables will consist of number of non-missing observations (n), mean, standard deviation (SD), minimum, 25th percentile, median, 75th percentile and maximum, unless specified otherwise. The precision of these variables is defined in the table, figure and listing shells document.

For categorical variables the number and percentage of patients in each category will be presented, based on the number of non-missing observations apart from disposition of patients, protocol deviations, background and demographic characteristics, prior and concomitant medications/procedures and adverse events where the percentage will be based on the number of patients in the analysis set.

Any statistical tests will be performed using a two-tailed 5% overall significance level, unless otherwise stated. The null hypothesis at all times will be that the treatments are equivalent. All comparisons between the treatments will be reported with 95% confidence intervals for the difference.

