6.2 General Derivations

This section provides details of general derivations. Detailed descriptions of specific parameter derivations are provided later in the SAP.

• Definition of baseline

The Baseline value will be defined as the pre-dose value on Day 1, if that is missing or the first administration is not on Day 1, it will be defined from the most recent value available and recorded prior to the first administration of study treatment.

Incomplete dates

For calculation purposes, incomplete dates will be completed using worst case, the most conservative value possible. For example, if the start date has a missing day value, the first day of the month will be imputed for study day computations. If day is

missing for an end date, the last day of the month will be imputed. Similar logic will be assumed for missing month and year components.

• Methods for handling withdrawals and missing data

There will be no imputation of missing data. Screening data will be used if baseline is missing.

Statistical testing and graphical presentations will not be carried out for any given score or measurement if there are less than 5 results, for either the placebo or active group, for that score or measurement at any single time point.

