6.10.2.1.1 Descriptive Summaries

Descriptive statistics for the total comfort score and the 14 day average comfort score will be presented along with the number and percentage of patients at each comfort classification will be presented for each treatment group for Days 1 to 14, Days 15 to 28, Days 29 to 42 and Days 43 to 56 for the recorded eye. The percentage will be out of the number of patients at each timepoint who had some data and therefore the total score could be calculated.

The percentage of missing data points will be summarised for each treatment group for Days 1 to 14, Days 15 to 28, Days 29 to 42 and Days 43 to 56.

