6.10.3.3 Rescue therapy

The number and percentage of patients that received a rescue medication (as indicated on the Concomitant Medications CRF page) at any stage of the trial (during Day 1 to Day 56 (last dose) and during Day 56 to Day 84 (follow-up visit) to be presented separately) and the number and percentage of patients that were receiving a rescue medication at the end of the trial (indicated as ongoing on the CRF) will be presented in a summary table by treatment group.

The number and percentage of patients that received a rescue medication will be presented for each treatment group for Days 1 to 14, Days 15 to 28, Days 29 to 42 and Days 43 to 56 to compliment the intervals for the efficacy analysis. The percentage will be out of the number of patients at each timepoint who had data for comfort scores to be calculated.

A patient is considered to have taken rescue medication during an interval where the start date (Day 1 or later) occurs during that interval, or if they continue to receive rescue medication that started in a previous interval.

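### SAP 6.10.2.1 leaves the comfort score with gaps between classes, a divisor undefined for partly recorded days, and two missing-data rules whose order is not stated

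*SAP*

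**What the plan says.** SAP 6.10.2.1 collects a score of 0 to 4 at five time points, morning and evening, and sums them over each 14-day period.

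- **Missing data.** An early sentence reads "If there are 20 or more missing data points during the period, then the total score will not be calculated and set to missing". The closing sentence, about sessions in which the five scores are not all available, rules out imputation and says that "the total score and classification will be derived for the two-week period for that patient regardless of missing data". SAP 6.10.2.1.1 bases the class percentages on "patients at each timepoint who had some data and therefore the total score could be calculated".
- **Average.** For totals that are not missing, the total is divided by the number of non-missing days. The SAP does not say how a partly recorded day counts.
- **Classes.** The average is classed as below 10, then "10 - 19 will be moderately uncomfortable, 20 - 29 will be very uncomfortable", then 30 or more. Protocol 6.9 has the same bands except at the top: "20 - 29 will be very uncomfortable and > 30 will be severely/unacceptably uncomfortable". The SAP text gives no rounding rule. SAP 6.1 says that "The precision of these variables is defined in the table, figure and listing shells document".
- **Use.** SAP 6.10.2.1.2 models the class by ordinal logistic regression, with a p-value for Days 43 to 56. SAP 6.2 adds a floor: "Statistical testing and graphical presentations will not be carried out for any given score or measurement if there are less than 5 results" in either arm at any single time point.
- **Rescue therapy.** For rescue use by two-week interval, SAP 6.10.3.3 states: "The percentage will be out of the number of patients at each timepoint who had data for comfort scores to be calculated". Rescue use itself is read from the Concomitant Medications page.

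SAP 6.17, which lists changes from the protocol, moves the comparison from weekly to two-weekly scores but settles none of these definitions.

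**The concern.** The class is the analysed outcome, so its derivation should be fixed before anyone sees treatment codes. As written, two programmers could take the same diary and reach different classes, or one could reach none. With about 8 patients per arm, one reclassified patient is 12.5% of an arm.

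The order of the two missing-data rules matters only for patient-periods with 20 or more missing points. There it decides whether a score exists and, through the five-result floor, it could decide whether the test is run at all. The base for the by-interval rescue percentages also depends on diary completeness, which has no bearing on whether rescue was taken.

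**Working it through.** Inputs are from SAP 6.10.2.1 unless stated: 5 time points, 2 sessions a day, 14 days, scores 0 to 4, cut-off 20 points. Part 2 has up to 16 patients randomised 1:1 (SAP 3 and 4), so 8 per arm.

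1. **The plan's own figures.** 5 × 2 × 14 = 140 points and 140 × 4 = 560. Both reproduce. The largest daily average is 560/14 = 40.

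2. **Class gaps.** A complete diary has an integer total T from 0 to 560 (561 values) and average T/14. 19 < T/14 < 20 holds for T = 267 to 279 (13 totals); 29 < T/14 < 30 holds for T = 407 to 419 (13 totals). So 26 of 561 totals (4.6%) have no class. An unstated rounding rule would not be neutral. Rounding and truncation disagree on 273–279 and 413–419 (14 of the 26), and rounding also lifts 133–139 from below 10 to 10.

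3. **The divisor.** Suppose every recorded point has the same value and some evenings are missed on separate days. *Any data* counts every day with at least one score. *Complete* counts only fully recorded days while keeping all recorded points in the total. *Per point* is 10 × sum / number of recorded points.

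| Score | Evenings missed | Any data | Complete | Per point |
|---|---|---|---|---|
| 1 | 0 | 140/14 = 10.00 | 10.00 | 10 |
| 1 | 1 | 135/14 = 9.64 | 135/13 = 10.38 | 10 |
| 1 | 3 | 125/14 = 8.93 | 125/11 = 11.36 | 10 |
| 2 | 1 | 270/14 = 19.29 (no class) | 270/13 = 20.77 | 20 |
| 2 | 3 | 250/14 = 17.86 | 250/11 = 22.73 | 20 |
| 3 | 1 | 405/14 = 28.93 | 405/13 = 31.15 | 30 |

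On the any-data reading, a session missed on a half-recorded day acts as scores of 0. With 19 points missing, the most the cut-off allows, the factor is 121/140 = 0.864, or −13.6%. On the complete-days reading, a constant 1 with one point missed on each of 7 days gives 133/7 = 19.0. One point missed on each of 14 days gives 126/0, with only 14 points missing. Whole missed days leave both numerator and divisor: a constant 1 over 12 full days gives 120/12 = 10, so they cause no bias.

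4. **Order of the rules.** Three missed sessions (15 points) are scored under either rule. Four sessions, or two whole days (20 points), are missing under the cut-off and scored under the closing sentence. If four of 8 patients in one arm reach 20 in a period, 8 − 4 = 4 results remain, below the floor of 5.

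5. **Days 43 to 56.** The end-of-dosing visit is Day 56 ± 2 days (Protocol 17.3). If dosing and diary stop on Day 54 after both sessions, 2 × 10 = 20 points are blank; if the Day 54 evening is also blank, 25 are.

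6. **Rescue base (illustrative counts).** With 2 rescued patients of 8, the figure is 25%. If two other patients have no score, it is 2/6 = 33%. If the two unscored patients are the rescued ones, it is 2/6 = 33% when they stay in the numerator and 0/6 = 0% when they leave it.

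**The case against.** The rules have a workable reading. The closing sentence concerns incomplete sessions, the cut-off concerns the whole period, and the average is defined only for totals that are not missing. Applied in that order, every sentence of SAP 6.10.2.1 can be followed, and the clause in SAP 6.10.2.1.1 ends by requiring that a total could be calculated. A reader might infer a flat contradiction. The documents show only that the order is unstated and that the reference to some data blurs it.

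The counts can also mislead. A gap total needs a mean score of about 1.9 (267/140) or 2.9 (407/140) per point for two weeks. In Protocol Table 5, 2 is already moderate and 3 severe discomfort. The examples in the table sit on class boundaries; elsewhere the same shift often changes no class. The complete-days figures are stress cases.

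The SAP has safeguards too: the percentage of missing points is tabulated, all diaries are listed, and SAP 6.10.2.1.2 allows alternative or sensitivity analyses according to the extent of missing data. The shells, not available here, may contain a rounding rule. Protocol 11.5 warns against undue weight on any single significant result.

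All this limits the impact. It does not define a non-missing day, close the class gaps in the SAP text or state the order of the rules. The discretion in SAP 6.10.2.1.2 leaves these choices open.

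**Conclusion.** The point holds as three faults of definition in a secondary, nominal endpoint, with a side effect on one rescue table. They should be fixed before unmasking. The primary ocular adverse event analysis is not affected.

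The class gaps follow directly from the text, subject to what the shells say about rounding. The divisor is unsound for partly recorded days on either reading: up to 13.6% too low if any day with data counts, too high or undefined if only complete days count. The order of the rules matters only at 20 or more missing points. The documents give no diary completeness figures, so the number of patients affected is unknown.

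Four stronger inferences are not supported:

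- Missed sessions are not always scored as 0. That needs a half-recorded day and the any-data reading.
- The 4.6% is a share of possible totals, not of patients.
- A Day 54 visit does not by itself trigger the cut-off. No text says that diaries stop there, and exactly 20 blank points requires both Day 54 sessions to be recorded.
- SAP 6.10.3.3 does not say that rescued patients without a score stay in the numerator. Only its by-interval percentages are affected; the any-stage and end-of-trial counts are not.

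**What to change.** Amend the SAP before unmasking:

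- **Limits:** below 10, 10 to below 20, 20 to below 30, and 30 or more, applied to the unrounded average. No total is then left without a class.
- **Average:** 10 × sum of recorded scores / number of recorded time points. For a complete diary this equals the current average.
- **Missing data:** state that the 20-point rule applies first and that the closing sentence of 6.10.2.1 covers only periods with fewer than 20 missing points. Reword the denominator in 6.10.2.1.1 to match.
- **Rescue by interval:** use Full Analysis Set patients still in the study at the start of each interval as the base in 6.10.3.3.

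First check diary completeness on masked, pooled data, including patients whose diary ends before Day 56 because of the visit window. If the five-result floor looks at risk, any change of threshold must be made then.

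The cost is SAP wording and a little programming, with no new data. One small downside is that the per-point average treats the 0.5- to 5-minute scores as interchangeable, which matters only if particular time points are missed selectively.

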6.10.2.1.2 Analysis

The classification of the average daily post-instillation comfort score will be analysed using an ordinal logistic regression model. The model will include treatment and visit as fixed effects and a treatment-by-visit interaction.

The following variance/covariance matrix structures for the repeated visits by a patient will be assessed: Compound symmetry, 1st order autoregressive, Toeplitz and unstructured. The variance/covariance matrix structure that results in the smallest Akaike information criterion (AIC), indicating the best model fit will be selected.

Assumptions about the proportionality of odds will also be assessed by appropriate methods such as by fitting fixed and random effects at each partition and testing the equality of the effects at different partitions. Should assumptions not hold, then the treatment odds ratios for the individual cumulative levels of the variable will be presented.

The adjusted least squares (LS) estimate for the treatment odds ratio (nomacopan:Placebo) along with corresponding 95% CI will be presented for each treatment period.

A null hypothesis of no change in classification of total post-instillation comfort score at Days 43 to 56 between treatment groups (nomacopan/Placebo) will be assessed and a p-value will also be reported.

The extent of missing data will be taken into consideration when analysing the total score data. Should it be felt appropriate, alternative analysis may be carried out and/or

sensitivity analyses using imputation methods such as last observation carried forward will also be considered.

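### SAP 6.10.2.1 gives two rules for a comfort score with 20 or more missing diary points and does not define the day count in its average

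*SAP*

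**What the plan says.** Under SAP 6.10.2.1, comfort is scored 0 to 4 at five times after each morning and evening instillation, and the scores are summed over each 14-day period. On missing scores the section says two things:

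- After defining the total: "If there are 20 or more missing data points during the period, then the total score will not be calculated and set to missing".
- In its last paragraph, for a morning or evening without all five scores: no imputation, and "the total score and classification will be derived for the two-week period for that patient regardless of missing data".

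Between the two it introduces the average: "For derived non-missing scores, an average score for the period will also be calculated as follows". The formula is the total divided by the number of non-missing days. The average is then put into one of four classes, the lowest being below 10 (comfortable).

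SAP 6.10.2.1.1 bases its percentages on patients "who had some data and therefore the total score could be calculated". SAP 6.10.2.1.2 states the model: "The classification of the average daily post-instillation comfort score will be analysed using an ordinal logistic regression model". It reports a p-value for Days 43 to 56. On missing data it adds "The extent of missing data will be taken into consideration when analysing the total score data", and it allows alternative or sensitivity analyses at discretion.

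SAP 6.10.3.3 takes rescue use from the Concomitant Medications page. For the two-week table it says: "The percentage will be out of the number of patients at each timepoint who had data for comfort scores to be calculated".

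**The concern.** A patient with 20 or more missing points in a period meets the conditions of both missing-data sentences. One blanks the score and the other derives it. The sentence followed decides whether that patient enters the ordinal model and the Days 43 to 56 test, the comfort tables in SAP 6.10.2.1.1 and 6.10.4, and the rescue denominator. It also feeds the SAP 6.2 rule that stops testing "if there are less than 5 results, for either the placebo or active group, for that score or measurement at any single time point".

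The day count is a separate gap and matters below the threshold too. A day has ten points in two sessions, and nothing says how a day with only one session enters the denominator. Because the classified average is the modelled outcome, the choice can move a patient across a cut-off. Protocol 11.1 leaves derivation algorithms and missing-data handling to the SAP, so no other text fills the gap.

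For rescue therapy, numerator and denominator come from different forms. A patient on rescue may have no comfort score, so the numerator need not be a subset of the denominator.

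**Working it through.** **1. The plan's own figures.** Points per period: 5 times x 2 sessions x 14 days = 140. Maximum total: 140 x 4 = 560. Both match SAP 6.10.2.1.

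**2. Where the two rules part.** 20 points / 5 per session = 4 of 28 sessions, or two whole days; 20/140 = 14.3%. The documents give no completion rate. Assume that sessions are missed independently, each with probability p. The chance of 4 or more missed sessions in a period is then:

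| p | Chance of reaching 20 points |
|---|---|
| 0.05 | 4.9% |
| 0.10 | 30.5% |
| 0.15 | 62.3% |
| 0.20 | 84.0% |

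**3. Text that bears on which rule governs.** For the 20-point rule: it is specific and mandatory, and the wording that introduces the average presupposes that some totals are missing. For the other reading: the last paragraph has no lower or upper limit, and SAP 6.10.2.1.1 infers that a total can be calculated from the presence of some data. SAP 6.2 says only that nothing is imputed. SAP 6.17 does not mention the issue.

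**4. The average when the 20-point rule does govern.** Example: three one-session days, so 15 points missing and 125 recorded, with an assumed total of 138.

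| A one-session day counts as | Days | Average | Class |
|---|---|---|---|
| 1 | 14 | 138/14 = 9.86 | comfortable |
| 0.5 | 12.5 | 138/12.5 = 11.04 | moderately uncomfortable |
| 0 | 11 | 138/11 = 12.55 | moderately uncomfortable |

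The middle row equals 10 x 138/125, the average per ten recorded points.

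**5. Size in general.** If every day has some data and counts as 1, the average is total/14. The point-based average is 10 x total/R, where R is the number of recorded points. Their ratio is R/140.

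- R = 125: 125/140 = 0.893, which is 11% low. The class below 10 then takes in point-based averages up to, but not including, 10/0.893 = 11.2.
- R = 121 (19 missing, the most the 20-point rule lets through): 121/140 = 0.864, which is 13.6% low. The limit becomes 10 x 140/121 = 11.57.
- One missed session with every recorded point scored 1: the total is 135. 135/14 = 9.64 (comfortable), against 10 x 135/135 = 10.0 (moderately uncomfortable).

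**6. The five-results check.** Assume 8 patients per arm (16 randomised 1:1). If 4 in one arm reach 20 missing points in the same period, that arm has 8 - 4 = 4 results under the 20-point rule, and the test is not run. Under the other sentence it has 8, and the test is run.

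**7. Rescue percentages.** Example: 2 of 8 on rescue is 25.0%. If one of the two has no comfort score, the figure becomes 2/7 = 28.6%, or 1/7 = 14.3% if that patient is also dropped from the numerator.

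**The case against.** **The two sentences can be reconciled.** The last paragraph can be read as covering an isolated incomplete session, which is at most 5 points and well under 20. If it overrode the threshold, the threshold would do nothing. This objection largely stands, and the 20-point rule is probably the intended one. It does not remove the need for a correction, because the text sets no such limit and the denominator in SAP 6.10.2.1.1 leans the other way.

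**The three day counts are not equally plausible.** Nothing in the SAP suggests half-days. Counting a part day as 0 keeps its scores in the numerator and drops the day from the denominator, which is unlikely to be meant. This stands. What remains is the most natural reading, that any day with data counts as 1, and that is the reading that understates the average.

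**The examples are constructed.** The total of 138 was chosen to lie near a cut-off, and step 6 needs half an arm to have large gaps in one period. This also stands.

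**Safeguards exist.** Diary cards are checked at each visit (Protocol 6.9.2). All diary data are listed (SAP 6.10.2.1.3), and totals and averages are shown by patient (SAP 6.10.4), so either rule could be re-derived for at most 16 patients. Protocol 11.5 warns against giving weight to any single significant result. These limit the damage but do not say which rule or day count is primary.

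**Stronger readings that a reader might infer.**

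- That a patient who records one session every day has the average halved. This needs both the last-paragraph rule and one-session days counted as 1 (70 points over 14 days). At 0.5 there is no halving, and at 0 the denominator is zero.
- That the withdrawal criteria in Protocol 7.2 show that such patients stay in the trial. Those criteria concern missed doses and visits. A patient can dose and not score, so they say little about diary gaps.

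**Conclusion.** The point holds and is minor. SAP 6.10.2.1 contains two missing-data rules that conflict as written at 20 or more missing points, with the 20-point rule the likely intention. Independently of that, the average is not fully defined. On the most natural day count it is low by 11% with three one-session days, and by up to 13.6% at the limit of 19 missing points. That can change the class that the model analyses. The rescue table has a denominator that does not match its numerator's source.

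The sizes rest on assumed diary patterns, on 8 patients per arm, and on missing points resembling recorded ones. The frequency is unknown and may be zero. A reader might infer that the comfort comparison is biased between arms or that the safety conclusion is at risk. The documents support neither: nothing shows that missing diary data would differ by arm, and the primary analysis of ocular treatment-emergent events does not use these scores. One secondary tolerability endpoint and one exploratory table are affected.

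**What to change.** Amend the SAP before unmasking:

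- **6.10.2.1, missing data:** state that total, average and classification are all missing when 20 or more of the 140 points are missing, and otherwise are derived without imputation. Delete the closing clause that derives them whatever is missing.
- **6.10.2.1, average:** define it as 10 x total / number of recorded points. A one-session day then counts as half a day, and isolated missing points are handled the same way. The small downside is that this assumes missing points resemble recorded ones. If mainly the later-minute scores are missing and discomfort fades, it overstates discomfort.
- **6.10.2.1.1:** base the percentages on patients with fewer than 20 missing points in that period.
- **6.10.3.3:** use as denominator the Full Analysis Set patients still in the study at the start of the interval. This also settles how to count someone who leaves during it.

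The cost is a few sentences of SAP wording and one derivation line. No protocol change and no new data are needed.

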6.9.2 Patient diary card

All patients will be issued with a diary card and will be asked to score comfort on a scale of 0 to 4 as shown in Table 5 below. The patient may make further comments (e.g. a difference in comfort between the two eyes) in the diary card.

| | Table 5 | Eye comfort scoring |
|--|---------|---------------------|
|--|---------|---------------------|

| Score | Description |
|-------|---|
| 0 | Perfectly comfortable |
| 1 | Slight discomfort. Aware of some burning, itching or stinging for up to half a minute after using the eye drop, solution but the discomfort improves without treatment. |
| 2 | Moderate discomfort. Burning, itching or stinging lasts for half a minute or longer but improves without treatment. |
| 3 | Severe discomfort. Burning, itching or stinging last for at least half a minute and requires washing the eyes to relieve it. |
| 4 | Unbearable burning itching or stinging. So severe that you cannot continue treatment. |

Scoring will be carried out at 0.5, 1, 2, 3 and 5 minutes after instillation of the drops and, in addition, patients will be asked to insert a brief description (up to 5 words) of how the eyes feel at the 3-minute time point. A list of suggested descriptor words will be provided but patients will be free to use any terminology they wish. Suggested descriptors are:

- Normal, cool, comfortable, smooth, fresh
- Uncomfortable, gritty, dry, sticky
- Burning, itchy, stinging, painful

In addition, there will be space for any other comments the patient may have.

Diary cards will be checked by the trial nurse or the PI/blind assessor at each visit to ensure that they are being filled in correctly and regularly.

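### The SAP's comfort classes can label brief or intermittent severe discomfort as comfortable, and patients who stop the drops drop out of the comfort tables and the only comfort test

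*SAP*

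**What the plan says.** Protocol 6.9.2 has patients grade comfort after instillation: "Scoring will be carried out at 0.5, 1, 2, 3 and 5 minutes after instillation of the drops". The SAP adds that this is done twice a day: "A score of 0 to 4 will be recorded at 0.5 min, 1 min, 2 min, 3 min and 5 min each morning and evening". Table 5 of the protocol defines the grades. Grade 1 begins "Slight discomfort. Aware of some burning, itching or stinging for up to half a minute after using the eye drop". Grade 3 is "Severe discomfort. Burning, itching or stinging last for at least half a minute and requires washing the eyes to relieve it". Grade 4 is "Unbearable burning itching or stinging. So severe that you cannot continue treatment".

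Protocol 6.9 sets the lowest band on a total whose period it does not define: "a total comfort score of < 10 will be deemed to be comfortable/acceptable". SAP 6.10.2.1 applies the bands (below 10, 10 to 19, 20 to 29, 30 or more) to each patient's average daily sum over a two-week period: "an average total comfort score of < 10 will be deemed to be comfortable/acceptable". SAP 6.17 records the move from weekly to two-weekly comparison but not this choice of scale.

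SAP 6.10.2.1.2 models the class in an ordinal logistic regression. It gives a treatment odds ratio with 95% CI for every period, but a test for one only: "A null hypothesis of no change in classification of total post-instillation comfort score at Days 43 to 56 between treatment groups". SAP 6.10.2.1 sets a period's total to missing when 20 or more of its 140 points are missing. Later in the same section it says that the total and class are derived whatever is missing. SAP 6.10.2.1.1 bases its percentages on patients whose total could be calculated.

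**The concern.** Safety and tolerability are the primary objective, and post-instillation comfort is the patient-graded tolerability measure among the secondary endpoints. A sum over ten readings measures total burden. It does not measure how bad the worst moment was, which is what Table 5 grades. Once the SAP attaches acceptability wording to the sum, a report could call the drops comfortable for a patient who recorded severe discomfort and washed the eyes after every dose.

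The second issue is who is counted. Table 5 itself expects that some discomfort will end treatment. Patients for whom this happens have no comfort class in the one period that is tested, and may have none in the period in which they stopped.

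**Working it through.** **The plan's own figures.** 5 readings × 2 instillations × 14 days = 140 points; 140 × 4 = 560; 560 / 14 = 40 per day. The first two match SAP 6.10.2.1. A daily average below 10 is a mean grade below 10 / 10 = 1.

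**Classes for a pattern repeated after every drop.** Daily average = 2 × (sum of the grades at 0.5, 1, 2, 3 and 5 minutes).

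| Pattern | Daily average | SAP class |
|---|---|---|
| 3-0-0-0-0 | 2 × 3 = 6 | comfortable |
| 3-1-0-0-0 | 2 × 4 = 8 | comfortable |
| 2-2-1-0-0 | 2 × 5 = 10 | moderately uncomfortable |
| 2-2-2-0-0 | 2 × 6 = 12 | moderately uncomfortable |
| 3-3-0-0-0 | 2 × 6 = 12 | moderately uncomfortable |
| 3-3-3-0-0 | 2 × 9 = 18 | moderately uncomfortable |
| 3-3-3-3-3 | 2 × 15 = 30 | severe |

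The first row fits Table 5: discomfort reaches half a minute and is gone at the next reading, as washing could achieve. It ranks better than patterns that never exceed grade 2.

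**Intermittent discomfort.** Grade 3 at all ten readings is 30 per day. On 4 of 14 days, with 0 otherwise, the average is 4 × 30 / 14 = 8.6, comfortable. On 5 of 14 days it is 5 × 30 / 14 = 10.7, moderately uncomfortable.

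**Patients who stop.** With an otherwise complete diary, a patient whose last dosed day in a period is day d has 10 × (14 − d) missing points. At d = 12 this is 20, so the total is set to missing; at d = 13 it is 10, and the total is kept. Stopping on day 12 or earlier therefore removes the period of stopping, including Days 1 to 14. Every later period has 140 of 140 missing, so there is no class at Days 43 to 56. Under the competing sentence in the same section, the period of stopping would be kept. The two sentences give different results for the same patient.

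**Effect on the test.** SAP 6.2 allows no test with fewer than 5 results in either group. With about 8 per arm (16 randomised 1:1), 4 stops in one arm leave 4 results and the test is not done.

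**The case against.** The strongest reply is that the failure is narrow. Among patterns that never rise after the first reading, only 2 of the 35 that start at grade 3 are classed comfortable. Prolonged grade 3 after every drop never is. Entrants have moderate to severe disease with itching and burning, so later readings may well be above 0, and nothing in the documents says they will mostly be 0. This stands as a limit on how often the label will be wrong. It does not remove the contradiction, because a count of possible patterns is not a frequency in patients, and the rule is wrong for the patterns shown.

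A reader might go further and infer that unbearable discomfort after every drop would be called comfortable. The sum does give 2 × 4 = 8 for grade 4 at the first reading only. But Table 5 defines grade 4 as being unable to continue, so two weeks of such records contradicts the definition. Nor is 1-1-1-1-1 (10 per day, moderately uncomfortable) a sound example of reversed order: grade 1 is limited to half a minute, so discomfort still present at 5 minutes fits it badly. The comparison of 3-0-0-0-0 with 2-2-2-0-0 does not depend on a late grade 1.

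On stopping, the SAP already gives odds ratios with 95% CIs for all periods. The model uses earlier periods, missingness is tabulated by arm, diary data are listed in full, and withdrawals and adverse events leading to discontinuation are summarised. The primary endpoint is ocular adverse events, and Protocol 11.5 treats secondary p-values as nominal. All of this softens the point. It does not put a patient who stopped back into the comfort percentages or the tested period. Carrying the last observation forward is only to be considered, and a patient who stopped by day 12 of the first period has no class to carry.

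**Conclusion.** The point holds in a limited form. As written, the rule places brief grade 3 discomfort after every drop (6 or 8 per day), and grade 3 all day on up to 4 of 14 days (8.6), in the class worded as comfortable, while some milder patterns are classed worse. This follows by arithmetic from the SAP rule and Table 5; it assumes complete diaries and, for the repeated patterns, the same record morning and evening. How many patients will show such patterns cannot be judged from the documents.

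Patients who stop have no class at Days 43 to 56 and are missing from the percentages, and may also lose the period in which they stopped. It is tempting to conclude that this favours the active drops. The documents do not support that: the direction depends on which arm has more stops, and no rate is given for either. Nor is early comfort left unanalysed, since estimates with intervals are planned for Days 1 to 14.

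The endpoint is secondary and the trial is not powered, so the change is worth making but the severity is modest.

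**What to change.** 1. In SAP 6.10.2.1, derive the peak Table 5 grade for each instillation. Report by arm and period each patient's worst grade and the proportion of instillations with a peak of 3 or more. Base any statement on acceptability on these. Keep the total and average as numeric summaries without comfort wording; the four bands can remain as unlabelled ordinal classes for the planned model. Record the departure from Protocol 6.9 in SAP 6.17.
2. In SAP 6.10.2.1.1 and 6.10.2.1.2, place a patient whose recorded reason for stopping the drops is discomfort in the highest ordinal class for the period of stopping and all later periods, overriding the 20-point rule. Report the p-value for Days 1 to 14 beside that for Days 43 to 56.
3. Reconcile the two missing-data sentences in SAP 6.10.2.1 so that one rule decides when a period has a class.

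The cost is a small extra derivation from diary data already collected, some rewording, and one entry in SAP 6.17. The drawback is that worst grade reacts to a single bad instillation, which is why the proportion is reported with it.
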